3.5.a. Eligibility: Participants must be 18 years or older; assigned ‘male’ at birth but currently identify as female, transgender, transsexual, or *travesti* (a common term for trans women in Brazil); not be known to be HIV positive; be a resident of the São Paulo area; and consent for study procedures, including review of clinical records. In Brazil, language that trans women use to describe themselves includes cultural terms such as ‘*transsexuais*’, ‘*mulher trans*’, and ‘*travesti*’ among others. No restrictions will be placed on the degree to which the participant has transitioned legally or physically. Participants may be PrEP-naïve or have initiated PrEP; being on PrEP is not an exclusion criterion. While we do not anticipate encountering many trans women already taking PrEP, preliminary data indicate that a large proportion of trans women who initiate PrEP will struggle with persistence and require renewed engagement¹⁹. Based on current data, we expect a maximum of 5% to have initiated PrEP prior to enrollment. We will not require HIV testing to enter the study; any participant who enrolls and either discovers she is positive or seroconverts will remain enrolled with navigation focused on HIV treatment. Recruitment staff will use a brief screening tool to establish eligibility prior to enrollment.

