3.5.b. Recruitment: Participants will be recruited from three sources over the course of 6 months: (1) those currently enrolled in the Trans*National Cohort in São Paulo; (2) trans women presenting for services at partnering clinics or presenting for HIV testing through the clinic run community-based programs; and (3) trans women recruited through targeted recruitment events. The Trans*National Cohort Study utilizes respondent-driven sampling (RDS) and has enrolled 565 HIV-negative women. Any participants not known to have seroconverted in the cohort will be invited to participate in *Guerreiras*. We expect to recruit approximately half of the participants through this method. We will also invite trans women testing negative for HIV at either SAE Campos Elíseos, the CRT, or through the community-based testing programs run by CRT to participate. The community-based testing program, called “Fique Sabendo” or “be in the know” is a state-run operation that visits areas where trans women work and congregate for testing. Finally, we will conduct recruitment events, advertised through trans-friendly locations, the PN team, and through social media, to ensure we reach trans women not seeking services or already in Trans*National. We aim to enroll half of the study participants through clinic partners and outreach events. (for details see Form E, Recruitment and Retention).

When a potential participant is interested in the study, staff will screen and enroll them, provide an appointment for screening and enrollment, or record preferred contact information to schedule an appointment. All participants will provide informed consent for study procedures, including clinical record extraction and PrEP eligibility exams (e.g. HIV and creatinine) if interested in PrEP, per national guidelines (see Human Subjects).

3.5.c. Randomization: Participants will be randomly assigned 1:1 to one of two arms using a computer generated “random order of assignment” list such that 200 will be assigned to the intervention arm and 200 will be assigned to the wait-list control arm. The random assignments will be placed in advance in sealed, numbered envelopes in each study location. To avoid potential bias based on timing or location of enrollment, we will use “block randomization,” with randomly-permuted block sizes to avoid identification of the allocation

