3.7 Measures

Primary Exposure: Randomization arm – intervention or wait-list control – will be considered the primary predictor variable for all primary analyses and recorded on study enrollment forms. Because the degree of engagement with the intervention will vary by individual, we will also capture intervention dose on study monitoring forms as a secondary exposure measure for additional (per protocol) analyses.

Primary Outcomes: (Evaluation: Aims 1 & 2): HIV testing uptake will be defined as any clinical evidence or report of HIV testing in each interval. This includes multiple data sources: documented HIV testing at a study clinic, report of having attended a non-study clinic for HIV testing, or evidence of HIVST kit receipt with self-report of HIVST use and/or documented HIVST use by the PN during a group or individual navigation session. The primary PrEP use outcome measure is PrEP *persistence*, which is the PrEP measure utilized for sample size calculations. We will document *PrEP initiation*, defined as a participant filling their first PrEP prescription, through PrEP dispensing information in the national SICLOM database. However, because initiation does not imply continued use, we will focus analyses of PrEP use on *PrEP persistence* – or documented use at every interval, defined as sufficient pill dispensation for complete 3-month coverage with no more than 10 days uncovered in the period. Secondary outcomes, including PrEP *adherence* and uptake of other prevention services (harm reduction, STI care) are listed in Table 3, below.

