Primary analyses for Aims 1 and 2. We expect HIV prevention outcomes to improve in the intervention arm relative to the control arm during the main trial phase. We hypothesize that, following the intervention, odds of HIV testing will be higher for intervention participants relative to control participants (Aim 1, Hypothesis 1). We also hypothesize that, following the intervention, the odds of PrEP initiation and persistence will be higher for the intervention group than for the control group (Aim 2, Hypothesis 2). Our primary interest is to estimate the marginal or population-average effects of intervention participation on these primary outcomes rather than the effect for a hypothetical average subject¹²⁶. Moreover, within-subject outcome correlations are considered nuisance parameters rather than quantities of interest to be modeled explicitly. Accordingly, generalized estimating equations (GEE) will be used for the primary analyses to test Hypotheses 1 and 2 using time-averaged comparisons of post-baseline (follow-up) measurements of intervention group with control group in the main trial phase. Alpha (α) will be set at .05 for these two planned comparisons. The alternating logistic

regression (ALR) approach implemented in SAS PROC GENMOD will be used to address the 3-level clustering of observations within participants and participants assigned to *Guerreiras* group leaders. This analysis will follow an intent-to-treat (ITT) approach by including all randomized participants. Further detail on the analytic model and secondary analyses, including secondary outcomes, intervention persistence, and intervention replicability, are included in Form E, Statistical Design and Power.

Primary Analyses for Aim 3. GEE will be used to test Aim 3 hypotheses that, following the intervention, relative to the control arm, intervention arm participants will have: 1) higher mean levels of resilience to anticipated stigma, 2) higher mean levels of resilience to enacted stigma, and 3) lower mean levels of internalized stigma. Analyses will follow the same ITT modeling approach as described above for Aims 1 and 2, except that a normal distribution and identity link will be employed to analyze continuous, normally-distributed stigma scores. These hypotheses will be tested via planned time-averaged comparisons of post-baseline measurements of the two arms in the main trial phase. These comparisons will be tested at $\alpha=.05$ per comparison.

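### The stated PrEP persistence analysis has no term for PrEP status at enrolment, which gives up precision, and women with earlier PrEP use stay in the initiation denominator although they cannot have the event

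*Combined protocol and SAP*

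**What the plan says.** - **Eligibility (3.5.a).** Women may be new to PrEP or have started it already: "being on PrEP is not an exclusion criterion". The plan adds "we expect a maximum of 5% to have initiated PrEP prior to enrollment", and justifies including these women because "a large proportion of trans women who initiate PrEP will struggle with persistence and require renewed engagement".
- **Randomisation (3.5.c).** "Participants will be randomly assigned 1:1 to one of two arms", in randomly permuted blocks with sealed envelopes at each location, so that "200 will be assigned to the intervention arm and 200 will be assigned to the wait-list control arm". PrEP status is not a stratification factor.
- **Persistence (3.7 and Table 3).** At least 80 covered days in each three-month interval, from SICLOM. It need not follow a new start.
- **Initiation (3.7).** It is "defined as a participant filling their first PrEP prescription". The Table 3 footnote calculates both PrEP outcomes among women with an indication and does not remove prior users.
- **Analysis (3.8).** GEE with "time-averaged comparisons of post-baseline (follow-up) measurements of intervention group with control group". No baseline PrEP term is stated, and Table 3 does not name earlier PrEP use among the covariates. Propensity or targeted-likelihood methods come in only if the arms differ significantly at baseline. Further model detail is left to Form E.
- **Power (3.8).** Control PrEP use of 5%, a detectable difference of 8 points, 300 women analysed, four follow-up measurements.

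**The concern.** A woman who enters with a current supply and keeps refilling meets the persistence definition at once. If quarters run from enrolment, only women on PrEP at entry or starting within about 10 days can be persistent in the first quarter. Intervention groups start only when enough women have enrolled and then run for 6–8 weeks, so early persistence will largely reflect status before randomisation.

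The assumed control rate (5%) equals the maximum share of prior users (5%). If a fraction q of prior users persists, they supply 0.05q/0.05 = q of the expected control-arm persistence. Enrolment status may therefore be a strong predictor of a rare primary outcome, and the stated model leaves its variation in the error.

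The initiation definition has a separate mismatch. Prior users are in the denominator but cannot have a first fill, and a restart, which is the plan's own reason for enrolling them, is not counted as initiation.

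**Working it through.** **1. The plan's own figure.** At two-sided 0.05 (sidedness is not stated) and 80% power, 5% versus 13% needs 200 women per arm for one observation each. With 150 per arm, power is 67.9% and the detectable difference is 9.6 points. With four visits, effective n per arm = 150 × 4/(1 + 3ρ)/(1 + 17.75 × ICC), where 17.75 = 150/8 − 1 assumes eight navigator pairs and applies clustering to both arms. It reaches 200 at ρ of about 0.67 with ICC 0, 0.52 with ICC 0.01, or 0.40 with ICC 0.02. The 8 points are plausible, but ρ and the ICC are not given, so they cannot be confirmed.

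**2. How uneven the split can be.** 5% × 400 = 20 prior users, allocated 200:200 (hypergeometric). The between-arm difference in their share has an SD of 2.2 points.

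| Split | Difference in share | Probability of this or worse, either direction |
|---|---|---|
| 13:7 | 6/200 = 3 points | 0.25 |
| 14:6 | 8/200 = 4 points | 0.11 |
| 15:5 | 10/200 = 5 points | 0.037 |

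The last column is also the exact two-sided P value for that baseline imbalance. A significance rule at 0.05 would act at 15:5, and not at 13:7 or 14:6.

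**3. Effect on the contrast.** Shift = difference in share × gap in persistence between prior users and the rest. For 13:7 this is 3 × 1.0 = 3 points with full persistence (and none among the others), 3 × 0.5 = 1.5 points with a 50-point gap, and 3 × 0.3 = 0.9 points with a 30-point gap.

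**4. Effect on power.** Let w = 0.05 be the prior-user share and q their persistence, taken as equal in both arms. Persistence among the others is r = (P − wq)/(1 − w). Unadjusted variance per woman is P(1 − P). Adjusted, it is wq(1 − q) + (1 − w)r(1 − r).

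Worked case, q = 0.6, 150 per arm:
- Control: r = (0.05 − 0.03)/0.95 = 0.0211. Variance falls from 0.0475 to 0.012 + 0.0196 = 0.0316.
- Intervention: r = (0.13 − 0.03)/0.95 = 0.1053. Variance falls from 0.1131 to 0.012 + 0.0895 = 0.1015.
- SE unadjusted = √[(0.0475 + 0.1131)/150] = 3.27 points; adjusted = √[(0.0316 + 0.1015)/150] = 2.98 points.
- Normal-approximation power: 8/3.27 − 1.96 = 0.49, about 69%; 8/2.98 − 1.96 = 0.72, about 77%.

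Simulation under the same assumptions (one value per woman, no clustering, stratum-standardised difference) gives slightly higher values at 150 per arm:

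| q | Unadjusted | Adjusted |
|---|---|---|
| 30% | 70% | about 72% |
| 40% | 70% | 73–74% |
| 60% | 70% | about 80% |
| 90% | 70% | about 95% |

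A second simulation used the mean over visits with within-woman correlation of about 0.8. It gave 76% to 78% at q = 30%, 76% to 83% at 50%, 74% to 89% at 70% and 73% to 98% at 90%. With no true effect and 200 per arm, type I error was 5.1–5.8% unadjusted and 4.7–5.3% adjusted.

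**5. Initiation.** If 5% of an arm cannot score, its rate is 0.95 times the rate among women with no earlier PrEP, a relative dilution of at most about 5%.

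**The case against.** **Prior use is not current use.** The 5% is a ceiling on women who ever initiated. Section 3.5.a expects few to be taking PrEP at entry and many to lapse. At q = 90%, persistence among all other controls would have to be (0.05 − 0.045)/0.95 = 0.5%. This stands: the 95% figure is an extreme. If only half of the 5% are current users and 60% of them persist (an assumption), power rises from 70% to 74%.

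**150 per arm may be too few.** Persistence comes from a national dispensing database and the analysis includes all randomised women, so a missed visit need not lose the outcome. At 200 per arm, unadjusted power is already about 82%, and adjustment gives about 84%, 89% and 98% at q = 40%, 60% and 90%. This also stands; a gain remains.

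**The term may exist.** Form E may contain a baseline PrEP covariate, and section 3.7 mentions covariates in general. A reader might infer that the model certainly lacks the term. The documents show only that none is stated.

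**Two stronger readings fail.** One is that the imbalance biases Aim 2. It does not, because a chance split is already in the standard error and type I error stays near 5%. The other is that 3 of the 8 points is the most that can be at risk. That figure is one split under full persistence: worse splits move the contrast more, and realistic lapse moves it less.

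**Initiation is a lesser measure.** Section 3.7 makes persistence the main PrEP outcome, and a restart with 80 covered days counts there. That limits the harm but leaves the denominator mismatch.

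**Conclusion.** The point holds as one of precision and definition, not of bias. The stated Aim 2 analysis omits a potentially strong predictor, and the contingent baseline rule would not respond to the imbalances most likely to matter. The gain from adjusting is about 2 to 4 points of power if 30–40% of prior users persist, about 10 points at 60%, and about 25 points only at 90%. These figures assume 20 prior users per 400, one value per woman, 150 per arm, no clustering, and a persistence rate that the documents do not give. Section 3.5.a points towards the lower end. If Form E already carries an enrolment PrEP term, the adjustment part is met. The initiation mismatch remains on the text of section 3.7 and Table 3, and is small.

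**What to change.** - **Section 3.8.** Pre-specify PrEP supply at enrolment (yes/no) as a covariate in the persistence GEE, whatever the baseline significance tests show. Take it from SICLOM dispensing dates, already a study data source under 3.6.b. Report the standardised (marginal) difference, because the coefficient of an adjusted logistic model is conditional on the covariate and the plan wants a population-average effect.
- **Section 3.7 and Table 3.** Calculate initiation among women with an indication and no PrEP dispensing before randomisation. Report restarts among prior users on a separate line.
- **Randomisation.** No change is needed. Stratifying would require a look-up before allocation and parallel envelope sets for about 20 women, and adds little beyond the covariate.

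The cost is one extra model term, a few lines of text and an initiation denominator smaller by at most about 5%. Both flags can be derived from the planned extracts after allocation, provided that only dispensing dated before randomisation is used.

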3.6. Data Collection

3.6.a Monitoring Visits and Surveys: The data collection schedule includes visits every 3 months: every other visit (every 6-months) will include a comprehensive survey (see Figure 2); all surveys are interviewer-administered on encrypted study tablets. At enrollment, participants will provide informed consent and then respond to the first (baseline) comprehensive survey. Participants will complete two additional comprehensive surveys (interim and endline) during the main trial phase. During the delayed intervention phase all participants will respond to an additional interim survey and wait-list control participants will also respond to a final (endline) survey at the end of the period. Comprehensive surveys will assess hypothesized covariates and mediators of our primary and secondary outcomes (see Table 3). Brief monitoring surveys (15 minute) to record outcomes at 3-month intervals will capture: self-reported HIV risk behaviors and risk reduction practices (condom use or partner reduction); HIV testing; PrEP use (including refills and adherence); other prevention services sought and utilized (STI testing and treatment, harm reduction). The endline survey will include questions about engagement in study activities and interactions with navigators. We utilize measures that have been validated in Brazil when possible, including those we have used in prior studies and those we are currently validating in Trans Amigas (see Measures section 3.7 for more detail). Participants will be reimbursed for all study visits.

Participants may choose to schedule visits at any of the three project sites, to optimize convenience. For those on PrEP, data collection visits will be scheduled at the participant's clinic to ensure that PrEP distribution, HIV testing, DBS collection, and survey data collection is integrated efficiently into clinical care. Study staff will be available at each site. For participants with difficulty presenting at a study location, staff will offer interviews by phone or WhatsApp, to minimize missing data, though all attempts will be made to maximize in-person data collection. Interviewers will be trained on interviewing techniques, standard operating procedures, and human subjects research, including ensuring complete confidentiality. (See Form E, Human Subjects for details).

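### Randomisation appears to be blocked by study location, but the primary model as described has no location term; pre-specifying one costs nothing and may recover some precision.

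*Combined protocol and SAP*

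**What the plan says.** Section 3.5.c allocates 1:1 from a computer-generated list, "such that 200 will be assigned to the intervention arm and 200 will be assigned to the wait-list control arm". It continues: "The random assignments will be placed in advance in sealed, numbered envelopes in each study location". The purpose of blocking is given as "To avoid potential bias based on timing or location of enrollment", and block sizes vary at random. The word stratified does not appear.

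Sections 3.3.b and 3.6.a describe three sites: two public clinics that offer HIV testing and PrEP, and a community office for women who would rather not use those clinics. Follow-up is not tied to the place of enrolment: "Participants may choose to schedule visits at any of the three project sites, to optimize convenience".

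Section 3.8 tests the primary hypotheses by GEE, "using time-averaged comparisons of post-baseline (follow-up) measurements of intervention group with control group in the main trial phase". Alternating logistic regression handles visits within women and women within group leaders. Location is neither a covariate nor a level. Under preliminary analyses, the same section brings in covariates only when the arms differ significantly on them at baseline. It also points elsewhere: "Further detail on the analytic model and secondary analyses, including secondary outcomes, intervention persistence, and intervention replicability, are included in Form E".

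**The concern.** If arms are balanced within locations by design, chance imbalance between locations contributes almost nothing to the true sampling error of the arm difference. A model without location does not know this. Its standard error still contains the between-location variance, so for this one feature the interval is wider than it need be.

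The plan's adjustment rule is unlikely to correct this. It is triggered by imbalance, and blocking is there to prevent imbalance on location. Adding location after the data are seen would be open to challenge.

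The locations could plausibly differ. Two of them provide testing and PrEP on site, the third serves women who avoid those clinics, and section 3.7 counts tests documented at a study clinic towards the outcome. What is at stake is precision. Omitting the term does not bias the arm comparison.

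**Working it through.** **1. The plan's own figures.** Inputs from section 3.8: 400 enrolled, 25% attrition, so 300 analysed (150 per arm); four post-baseline measurements; α = .05 (sidedness not stated, two-sided assumed); power .80; detectable differences of 13 points from .50 (HIV testing) and 8 points from .05 (PrEP). The within-woman correlation ρ and the navigator-pair ICC are not given.

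The usual two-proportion formula needs 228 per arm for .50 v .63 and 200 per arm for .05 v .13. Averaging four visits multiplies the variance by (1 + 3ρ)/4. With no clustering, 150/228 = 0.658 implies ρ = (4 × 0.658 − 1)/3 ≈ 0.54, and 150/200 = 0.75 implies ρ ≈ 0.67. Sixteen navigators (section 3.4.e) make 8 pairs, or 150/8 = 18.75 women per pair, so the design effect is 1 + 17.75 × ICC (applied here to both arms for simplicity). At ρ = 0.5 and ICC .005 to .01, the detectable differences are 13.2 to 13.7 and 7.5 to 7.9 points. The stated figures cannot be reproduced exactly, but they are plausible.

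**2. Location's share of variance.** Assume three equal locations with rates p₁, p₂, p₃ and mean p. For a woman's four-visit mean,

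R = [Σ(pᵢ − p)²/3] / [p(1 − p)(1 + 3ρ)/4].

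With arms balanced within location and planned power of 80% (1.960 + 0.8416 = 2.8016):

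- type I error without location = 2[1 − Φ(1.960/√(1 − R))]
- power without location = Φ(0.8416/√(1 − R))
- power with location = Φ(2.8016/√(1 − R) − 1.960)

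Example, 40/50/60% at ρ = 0.5: R = 0.00667/0.15625 = 0.043 and √(1 − R) = 0.978. Type I error is .045; power is Φ(0.860) = 80.5% without location and Φ(0.903) = 81.7% with it.

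All location rates below are assumptions (ρ = 0.5).

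| Outcome | Rates by location | R | Type I error, no location term | Power without / with location |
|---|---|---|---|---|
| HIV testing | 50/50/50% | 0 | .050 | 80.0 / 80.0% |
| HIV testing | 45/50/55% | .011 | .049 | 80.1 / 80.4% |
| HIV testing | 40/50/60% | .043 | .045 | 80.5 / 81.7% |
| HIV testing | 35/50/65% | .096 | .039 | 81.2 / 83.8% |
| HIV testing | 30/50/70% | .171 | .031 | 82.2 / 86.8% |
| PrEP persistence | 3/5/7% | .009 | .049 | 80.1 / 80.4% |
| PrEP persistence | 2/5/8% | .020 | .048 | 80.2 / 80.8% |
| PrEP persistence | 0/5/10% | .056 | .044 | 80.7 / 82.2% |

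At ρ = 0.8 the gains shrink: 80.4 against 81.2% for 40/50/60%, and 81.6 against 85.0% for 30/50/70%.

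**3. Simulation.** With 20,000 runs, 50 women per arm per location and ρ = 0.5, type I error without and with location was .047 and .054 (40/50/60%), and .034 and .054 (30/50/70%). Power at 13 points was 82.3 against 83.5%, and 82.4 against 87.1%. When allocation was not blocked by location, the 40/50/60% case gave .049 without a location term, so the low type I error depends on location-specific lists.

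A second simulation (4,000 trials per setting, 25% random loss, ρ = 0.3, 10-point effect) gave 68 against 75% power for rates of 65/55/30%, and 71 against 73% for 60/50/40%.

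**4. Clustering on navigator pairs.** Step 3 ignores the planned clustering. With a sandwich standard error clustered on 8 pairs in the intervention arm and no location term, null rejection was 6.6% when locations did not differ and 6.5% at 40/50/60%. With a pair ICC of .02 the figures were 7.5% and 6.9%. At 30/50/70% without a pair effect it was 5.3%.

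**The case against.** A reader might infer that the primary test runs below its 5% level and that the trial loses planned power on both primary outcomes. The documents do not support that, for five reasons.

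- Form E holds further detail on the model and may contain a location term. Its absence is established only for the text supplied.
- Location-specific lists are inferred from the envelopes and the stated purpose of blocking. They are not declared.
- No rates by location are given, and location may be a weak marker of service use. About half the sample is to come from an existing cohort whose research site is one of the clinics, and self-tests and tests at other clinics also count. If rates do not differ, nothing is lost.
- The power statement in section 3.8 claims no benefit from location adjustment, so omitting the term takes nothing from it. For PrEP at 5% there is little between-location variance to remove.
- Clustering on 8 navigator pairs can push type I error above 5%, so the net direction for the full planned test is not known.

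All five stand, and they limit the claim to forgone precision. They do not supply a reason to leave out a factor that the randomisation appears to balance.

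**Conclusion.** The point holds as a free improvement. The supplied text implies blocking by location and describes a primary model without it, and the adjust-if-imbalanced rule would rarely bring it in. If location predicts the outcome, precision is forgone. For HIV testing this is about 0 to 2 power points for location spreads of up to 20 points, 2.6 points at 35/50/65%, and about 4 to 7 points for spreads of 35 to 40 (3.4 at 30/50/70% if ρ is 0.8). For PrEP persistence it is usually under 1 point and at most about 1.5. These sizes rest on assumed location rates and correlations, equal-sized locations in the table, and no navigator-pair effect. No bias, shortfall in stated power or overall conservatism is shown.

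**What to change.** In section 3.5.c, state that a separate permuted-block list is used at each study location, if that is the case. In section 3.8, unless Form E already says so, add wording such as: the primary models include enrolment location as a fixed effect, defined as the location whose envelope list was used and not the site later visited, and the marginal arm effect is obtained by standardising over location.

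The definition matters because women may attend any of the three sites during follow-up. Standardising matters because, with a logit link, the adjusted coefficient is conditional on location, whereas section 3.8 asks for a population-average effect. Because PrEP persistence is assumed to be rare, the text should also say what is done if a location has no events. The cost is a few sentences and two model parameters, with no new data.
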